4.6.2. Benefit Assessment

This Phase I study is being conducted in healthy subjects; therefore, there is no direct clinical benefit to study subjects. Participation in this study may contribute to the process of developing new therapies in an area of unmet need.

4.6.3. Overall Benefit:Risk Conclusion

The risk of AEs is minimized for the population being investigated in the proposed study by careful selection of subjects for the study and the extent of safety monitoring incorporated into the study.

5. SELECTION OF STUDY POPULATION AND WITHDRAWAL CRITERIA

Specific information regarding warnings, precautions, contraindications, AEs, and other pertinent information on the GSK investigational product or other study treatment that may impact subject eligibility is provided in the IB [GSK Document Number [2015N255155_00](#)].

Deviations from inclusion and exclusion criteria are not allowed because they can potentially jeopardize the scientific integrity of the study, regulatory acceptability, or subject safety. Therefore, adherence to the criteria as specified in the protocol is essential. A single repeat for clinical laboratory tests that meet the exclusion criteria may be conducted to confirm the value before the subject is excluded from the study.

5.1. Inclusion Criteria

A subject will be eligible for inclusion in this study only if all of the following criteria apply:

AGE
1. Between 18 and 55 years of age, inclusive, at the time of signing the informed consent.

TYPE OF SUBJECT AND DIAGNOSIS INCLUDING DISEASE SEVERITY
2. Healthy as determined by a responsible and experienced physician, based on a medical evaluation including medical history, physical examination, laboratory tests and cardiac monitoring. A subject with a clinical abnormality or laboratory parameter outside the reference range for the population being studied may be included only if the investigator feels and documents that the finding is unlikely to introduce additional risk factors and will not interfere with the study procedures.
3. Additional inclusion criteria for Japanese subjects (Part 3 only): 
 • The subject is a non-naturalized Japanese citizen and holds a Japanese passport. • The subject has 2 Japanese parents and 4 Japanese grandparents who are non-naturalized Japanese citizens, as confirmed by interview.

- The subject has been living outside of Japan for less than 10 years, as confirmed by interview.

WEIGHT

4. Body weight >50 kg (110 lb) for men and >40 kg (99 lb) for women and body mass index within the range of 18.5 to 30 kg/m², inclusive.

SEX

5. Male or Female

Males:

Male subjects with female partners of child-bearing potential must agree to use one of the highly effective contraception requirements listed in [Appendix 8](#) from the time of first dose of study drug until completion of the Follow-up visit.

Females:

A female subject is eligible to participate if she is not pregnant (as confirmed by a negative serum human chorionic gonadotropin [hCG] test), not lactating, and considered to be of non-reproductive potential.

Non-reproductive potential is defined as:

- Pre-menopausal females with one of the following:
 - Documented tubal ligation
 - Documented hysteroscopic tubal occlusion procedure with follow-up confirmation of bilateral tubal occlusion
 - Hysterectomy
 - Documented bilateral oophorectomy
- Postmenopausal defined as 12 months of spontaneous amenorrhea and in questionable cases a blood sample with simultaneous follicle-stimulating hormone (FSH) and estradiol levels consistent with menopause (refer to laboratory reference ranges for confirmatory levels).
- Females on hormone replacement therapy (HRT) and whose menopausal status is in doubt will be required to use one of the highly effective contraception methods listed in [Appendix 8](#) if they wish to continue their HRT during the study. Otherwise, they must discontinue HRT to allow confirmation of post-menopausal status before study enrolment.

INFORMED CONSENT

6. Capable of giving signed informed consent as described in Section [10.2](#), which includes compliance with the requirements and restrictions listed in the consent form and in this protocol.

5.2. Exclusion Criteria

A subject will not be eligible for inclusion in this study if any of the following criteria apply:

CONCURRENT CONDITIONS/MEDICAL HISTORY (INCLUDES LIVER FUNCTION AND QTc INTERVAL)

1. Alanine aminotransferase (ALT) not within normal limits; bilirubin $>1.5\times$ upper limit of normal (ULN; isolated bilirubin $>1.5\times$ ULN is acceptable if bilirubin is fractionated and direct bilirubin is $<35\%$).
2. Current or chronic history of liver disease, or known hepatic or biliary abnormalities (with the exception of Gilbert's syndrome or asymptomatic gallstones).
3. Corrected QT (QTc) >450 msec.
4. Any clinically significant central nervous system (e.g., seizures), cardiac, pulmonary, metabolic, renal, hepatic, or gastrointestinal condition or history of such a condition that, in the opinion of the investigator, may place the subject at an unacceptable risk as a participant in this trial or may interfere with the absorption, distribution, metabolism, or excretion of drugs.
5. Use of a systemic antibiotic within 30 days of screening.
6. Ongoing febrile illness.
7. Confirmed history of *Clostridium difficile* diarrhea (see [Appendix 10: Clostridium difficile Testing Procedure and Algorithm](#)).

CONCOMITANT MEDICATIONS

8. Unable to refrain from the use of prescription or non-prescription drugs, including vitamins, herbal and dietary supplements (including St John's Wort) within 7 days (or 14 days if the drug is a potential enzyme inducer) or 5 half-lives (whichever is longer) before the first dose of study treatment, unless in the opinion of the Investigator and the GSK medical monitor, the medication will not interfere with the study procedures or compromise subject safety.

RELEVANT HABITS

9. History of regular alcohol consumption within 6 months of screening defined as an average weekly intake of >21 units (or an average daily intake of >3 units) for males or an average weekly intake of >14 units (or an average daily intake >2 units) for females. One unit is equivalent to 270 mL of full strength beer, 470 mL of light beer, 30 mL of spirits, or 100 mL of wine.
10. Urinary cotinine level indicative of smoking or history or regular use of tobacco- or nicotine-containing products within 3 months before screening.

CONTRAINDICATIONS

11. History of hypersensitivity attributed to β -lactam antibiotics (including cephalosporin, carbapenem, or penicillin antibiotics) or other drugs, a history of multiple antibiotic intolerances, or a history of serious adverse drug reactions.
12. Sensitivity to poison ivy or other catechol-related hypersensitivity (e.g., mango allergy).
13. History of sensitivity to heparin or heparin-induced thrombocytopenia.
14. History of latex allergy.
15. History of sensitivity to any of the study treatments or components thereof, or a history of drug or other allergy that, in the opinion of the investigator or medical monitor, contraindicates participation in this study.

DIAGNOSTIC ASSESSMENTS AND OTHER CRITERIA

16. Presence of hepatitis B surface antigen or positive hepatitis C antibody test result at screening or within 3 months before the first dosing day in this study.
17. Serum creatinine >ULN.
18. Glomerular filtration rate <90 mL/min/1.73m² as calculated by the Chronic Kidney Disease Epidemiology Collaboration formula (See [Appendix 11](#)).
19. Albumin to creatinine ratio (ACR) >0.03 mg/mg. In the event of an ACR above this threshold, eligibility may be confirmed by a second measurement.
20. Urinalysis positive for blood without other cause identified.
21. A positive pre-study drug or alcohol screen.
22. A positive test for human immunodeficiency virus antibody at or before screening.
23. Where participation in the study would result in donation of blood or blood products in excess of 500 mL within a 56-day period.
24. The subject has participated in a clinical trial and has received an investigational product within the following time period before the first dosing day in this study: 30 days, 5 half-lives or twice the duration of the biological effect of the investigational product (whichever is longer).
25. Exposure to more than 4 new chemical entities within 12 months before the first dosing day in this study.
26. Exclusion criteria for screening and baseline 12-lead ECG (a single repeat is allowed for eligibility determination):

	Males	Females
Heart rate	<40 and >100 beats per minute	<50 and >100 beats per minute
PR interval	<120 and >220 msec	
QRS duration	<70 and >120 msec	
QTcB or QTcF interval	>450 msec	
QTcB = corrected QT interval using Bazett's formula, QTcF = corrected QT interval using Fridericia's formula.		

- a) Evidence of previous myocardial infarction (does not include ST segment changes associated with repolarization).
- b) Subject has bundle branch block.
- c) Any conduction abnormality (including but not specific to left or right complete bundle branch block, AV block [2nd degree or higher], Wolf-Parkinson-White

syndrome), sinus pauses more than 3 seconds, non-sustained or sustained ventricular tachycardia (≥ 3 consecutive ventricular ectopic beats), or any significant arrhythmia that, in the opinion of the investigator and the GSK medical monitor, will interfere with the safety of the individual subject.

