Renal findings	
 • Kidney: hyaline droplets in proximal tubules, weight increase in both species 
 • Hyaline droplets associates with absorption and secretion of the cephem antibiotics in lysosome • No degenerative changes • Probably mixture of drug and protein (stimulation of lysosomal turnover) • Accompanied by increases in urinary N-acetyl-β-D-glucosaminidase (exploratory biomarker of lysosomal enzyme) at all doses and slight change in urinary albumin at 2000 mg/kg (relevance unclear) 	
 • Inclusion/Exclusion 
 • Healthy subjects • Serum creatinine greater than the upper limit of normal (ULN) • Estimated glomerular filtration rate (eGFR) <90 mL/min/1.73 m² as calculated by the Chronic Kidney Disease Epidemiology Collaboration formula • Albumin to creatinine ratio (ACR) ≥0.03 mg/mg • Urinalysis negative for blood/protein • Monitor: 
 • Serum blood urea nitrogen, creatinine, eGFR, electrolytes, urinalysis • ACR during the study • Criteria to pause Part 1 progression or interrupt Part 2 dosing 
 • Creatinine change >0.3 mg/dL without alternative cause • New blood in urinalysis confirmed by microscopy without alternative cause • ACR ≥0.03 mg/mg
Injection site reactions	
 • Local irritation 
 • Gross: discoloration, hardening, wound, thrombosis • Histology: ulcer, perivascular/vascular inflammation, thrombus (1000/2000 mg/kg/day; rats and monkeys) • Considered due to high osmolality of the dosing formulations 	
 • Reduced osmolality preparation • Monitor injection site including proximal limb for vascular change

Potential Risk of Clinical Significance	Summary of Data/Rationale for Risk	Mitigation Strategy

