5.4. Withdrawal/Stopping Criteria

The following actions must be taken in relation to a subject who fails to attend the clinical unit for a required study visit:

- The site must attempt to contact the subject and re-schedule the missed visit as soon as possible.
- The site must counsel the subject on the importance of maintaining the assigned visit schedule and ascertain whether or not the subject wishes to and/or should continue in the study.
- In cases where the subject is deemed ‘lost to follow up’, the investigator or designee must make every effort to regain contact with the subject (where possible, 3 telephone calls and if necessary a certified letter to the subject’s last known mailing address or local equivalent methods). These contact attempts should be documented in the subject’s medical record.
- Should the subject continue to be unreachable, only then will he/she be considered to have withdrawn from the study with a primary reason of “lost to follow up”.

A subject may withdraw from study treatment at any time at his/her own request, or may be withdrawn at any time at the discretion of the investigator for safety, behavioral, or administrative reasons. If a subject withdraws from the study, he/she may request destruction of any samples taken, and the investigator must document this in the site study records.

This protocol defines several clinical laboratory values, 12-lead ECG values, vital sign values, and additional safety criteria that, if observed and confirmed, mandate cessation of drug dosing and further evaluations. Any laboratory result that meets the stopping criteria should be repeated once to confirm the value before the subject is withdrawn from the study.

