5.4.3. Renal Stopping Criteria

Study treatment will be discontinued for a subject who meets any of the following criteria:

- Persistent (confirmed on recheck) elevation of serum creatinine (>0.3 mg/dL) without an alternative cause identified
- Albumin to creatinine ratio ≥ 0.03 mg/mg
- New blood in urinalysis confirmed by microscopy without an alternative cause identified

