Genetic sample		X	Collect a pharmacogenomics sample only if the subject has a signed consent specific for this purpose. The pharmacogenomics sample can be collected anytime, but Day -1 is recommended. Informed consent for optional sub-studies (e.g., genetics research) must be obtained before collecting a sample.
Admission to clinical unit		X	
β -hCG = beta human chorionic gonadotropin, BP = blood pressure, FSH = follicle-stimulating hormone, HR = heart rate, KIM-1 = kidney injury molecule 1, NGAL = neutrophil gelatinase-associated lipocalin, SAE = serious adverse event.			

Table 4 Time and Events Table: Part 1 - Single Dose Escalation and Part 3 - Single Dose

Procedure	Day 1																	Day 2	Day 3	
	Hours relative to treatment administration																			
	Pre-dose	0	0.5	1	1.25	1.5	2	3	3.5	4	4.5	5	6	8	10	12	16	24	36	48
Randomization	X																			
12-lead ECG ¹	X		X	X		X	X	X		X			X			X		X		X
Vital signs (BP, HR, oral temperature, respiration rate)	X		X	X		X	X	X		X			X			X		X		X
Fasting clinical chemistry, hematology, and urinalysis ²																		X		
Treatment administration ³		X																		
Blood collection for pharmacokinetics ⁴	X		X	X	X	X	X	X	X	X	X	X	X	X	X	X	X	X	X	X
Urine collection for pharmacokinetics ⁵	X	X								X				X		X		X		X
Continuous cardiac monitoring ⁶	X	-----Continuous review----->																		
AE review		X	-----Continuous review----->																	
SAE review	X	-----Continuous review----->																		
Concomitant medication review	X	-----Continuous review----->																		
Discharge from inpatient unit ⁷																				X

AE = adverse event, BP = blood pressure, ECG = electrocardiogram, HR = heart rate, SAE = serious adverse event.

NOTES:

1. Triplicate 12-lead ECGs to be obtained at least 5 minutes apart within 1 hour before dosing. Single ECGs will be obtained at all other time points.
2. An aliquot of the urine sample will be collected for neutrophil gelatinase-associated lipocalin (NGAL) and kidney injury molecule 1 (KIM-1). These samples may be analyzed after the end of the study if a clinical signal is detected. Instructions for collection and storage of these urine samples are included in the Study Reference Manual. The albumin to creatinine ratio will be determined using the first morning void urine on Day 2.
3. GSK3342830 or placebo will be administered as a single IV infusion in the morning on Day 1. The planned infusion duration time is 1 hour.

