AE = adverse event, BP = blood pressure, ECG = electrocardiogram, HR = heart rate, SAE = serious adverse event.

NOTES:

1. Triplicate 12-lead ECGs will be obtained at least 5 minutes apart within 1 hour before the start of infusion (pre-dose) on Day 1. Single ECGs will be obtained at 0.5, 1, 1.5, 2, 3, 4, 6, and 12 hours after the start of infusion on Day 1 and Day 15, within 1 hour before the start of the morning infusion on Days 2, 3, 4, 5, 6, 7, 8, 9, 10, 11, 12, 13, and 14, and in the morning on Day 16.
2. Vital signs will be measured within 1 hour before the start of infusion (pre-dose) and at 0.5, 1, 1.5, 2, 3, 4, 6, and 12 hours after the start of infusion on Days 1 and 15, within 1 hour before the start of the morning infusion and on Days 2, 3, 4, 5, 6, 7, 8, 9, 10, 11, 12, 13, and 14, and in the morning on Day 16.
3. An aliquot of the urine sample will be collected for neutrophil gelatinase-associated lipocalin (NGAL) and kidney injury molecule 1 (KIM-1). These samples may be analyzed after the end of the study if a clinical signal is detected. Instructions for collection and storage of these urine samples are included in the Study Reference Manual. Hematology assessments on Days 5 and 15 will also include total iron, total iron binding capacity, ferritin, haptoglobin, ceruloplasmin and reticulocytes. The albumin to creatinine ratio will be determined using the first morning void urine on Days 5 and 15. Urinalysis assessments before dosing on Day 15 will also include urine color.
4. GSK3342830 or placebo will be administered as a single IV infusion in the morning on Day 1, TID IV infusions (approximately every 8 hours) on Days 2, 3, 4, 5, 6, 7, 8, 9, 10, 11, 12, 13, and 14, and as a single IV infusion in the morning on Day 15. The planned infusion duration time is 1 hour.

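### An ACR of exactly 0.03 mg/mg is eligible under exclusion criterion 19, ineligible under Section 4.6.1, and already at the renal stopping limit

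*Protocol*

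**What the plan says.** Three sections of the protocol set limits on the urinary albumin to creatinine ratio (ACR), all at 0.03 mg/mg.

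- **Eligibility, Section 5.2, item 19.** The exclusion reads "Albumin to creatinine ratio (ACR) >0.03 mg/mg. In the event of an ACR above this threshold, eligibility may be confirmed by a second measurement". Section 5 makes the criteria binding: "Deviations from inclusion and exclusion criteria are not allowed".
- **Risk table, Section 4.6.1, renal findings.** The entry limits include "Albumin to creatinine ratio (ACR) ≥0.03 mg/mg". The same cell then has a list introduced as "Criteria to pause Part 1 progression or interrupt Part 2 dosing", which also uses ACR at or above 0.03 mg/mg.
- **Individual stopping, Section 5.4.3.** Study treatment is discontinued at "Albumin to creatinine ratio ≥ 0.03 mg/mg". The creatinine and haematuria criteria in that list apply only if no other cause is found. The ACR criterion has no such qualifier and no change-from-baseline condition.

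Section 5.4 adds a general repeat rule: "Any laboratory result that meets the stopping criteria should be repeated once to confirm the value before the subject is withdrawn from the study". The on-study schedule is in the notes to the tables in Section 7.1. For Part 2, "The albumin to creatinine ratio will be determined using the first morning void urine on Days 5 and 15". For Parts 1 and 3, "The albumin to creatinine ratio will be determined using the first morning void urine on Day 2".

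**The concern.** The inequality signs do not match. Item 19 is strict and the other three limits are not, so a subject at exactly 0.03 mg/mg is accepted by the criterion the site applies, rejected by the risk table, and already at the level that ends treatment.

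ACR is monitored because slight changes in urinary albumin were seen in animals at 2000 mg/kg, the dose whose exposures define the human exposure limits. A pause or discontinuation that only reflects the value at entry could be mistaken for a renal effect of the drug. The stopping rule covers placebo subjects too, and site staff do not know the assignment. At stake are an avoidable loss of repeat dosing in Part 2, or an avoidable pause in Part 1.

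**Working it through.** The documents give no figure to reproduce. The check sets the limits side by side and then counts the infusions an affected subject could lose.

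**Step 1. Apply each rule at ACR = 0.03 mg/mg.**

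| Rule | Condition | At 0.03 | Result |
|---|---|---|---|
| 5.2 item 19, exclusion | ACR > 0.03 | false | eligible |
| 4.6.1, entry limit | ACR ≥ 0.03 | true | not eligible |
| 4.6.1, pause or interrupt | ACR ≥ 0.03 | true | pause Part 1 or interrupt Part 2 |
| 5.4.3, stopping | ACR ≥ 0.03 | true | discontinue |

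The eligible set under 5.2 is ACR ≤ 0.03 and the stopping set under 5.4.3 is ACR ≥ 0.03. They overlap at the single value 0.03. The two entry rules disagree at that value only.

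**Step 2. See whether a repeat rule closes the gap.** Item 19 offers a second measurement only for a reading above the limit, so a reading of 0.03 does not trigger it. The repeat in Section 5.4 protects against a chance high reading, but a subject whose stable value is 0.03 meets the rule again. The only scheduled pre-dose ACR is at Screening, up to 30 days before Day 1.

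**Step 3. Count the Part 2 infusions** (schedule from Section 4.1).

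- Planned: 1 on Day 1, 13 × 3 = 39 on Days 2 to 14, and 1 on Day 15. Total 1 + 39 + 1 = 41.
- Given before Day 5: 1 + 3 × 3 = 10.
- Stop at the Day 5 reading, before that morning's infusion: 41 − 10 = 31 lost; 31/41 = 75.6%.
- Stop on the morning of Day 6, assuming the repeat takes one day: 13 given, 41 − 13 = 28 lost; 28/41 = 68.3%.
- Stop at the Day 15 reading: at most 1 lost; 1/41 = 2.4%.

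**Step 4. Parts 1 and 3.** There is one infusion, on Day 1. The first post-dose ACR is on Day 2, so 0 infusions are lost. A pause in Part 1 progression under 4.6.1 remains possible.

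**Step 5. Effect on escalation.** A Part 2 cohort has about 8 active subjects. Losing one leaves 8 − 1 = 7, against the approximately 5 needed before the next dose level.

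**Step 6. Reporting precision.** The documents do not give it. If results are rounded to two decimals (assumption), a reported 0.03 covers true values of about 0.025 to 0.035. With three decimals, 0.030 covers about 0.0295 to 0.0305. The coarser the reporting, the more often the boundary value will occur.

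**The case against.** The strongest reply accepts that the signs differ and disputes the weight.

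- **Section 4.6.1 is a summary.** It paraphrases other criteria loosely. It asks for QTc below 450 msec where 5.2 excludes above 450, and for urinalysis free of blood and protein where item 20 excludes blood only. A site works from 5.2, so the mismatch with 4.6.1 taken alone is editorial. This stands, but it does not remove the overlap between 5.2 and 5.4.3, both of which are operative.
- **A screening value is not an on-study value.** Screening may be up to 30 days before dosing and may use urine passed at the visit, whereas on-study ACR uses the first morning void. A subject at 0.03 at Screening need not read at or above 0.03 on Day 5. This stands, so the infusion losses are conditional on a stop. They are not expected losses.
- **The 76% figure is a worst case.** It needs the boundary value at entry, Part 2, a Day 5 reading at or above the limit, and no dosing while the repeat is done. This also stands.
- **The fix is narrow.** A subject at 0.029 can still cross an absolute limit through ordinary variation. This is true. The change removes the contradiction at 0.03 but leaves entry and stopping limits next to each other.

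Nothing in the reply reconciles the three sections at 0.03.

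**Conclusion.** The concern holds. Item 19 is inconsistent with Section 4.6.1 and overlaps the stopping rule in Section 5.4.3 at 0.03 mg/mg, and no other text in the protocol resolves this.

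The practical impact is low. The documents do not say how many subjects would read exactly 0.03; the number is probably very small and depends on the unstated reporting precision. The consequence is mainly a possible Part 2 discontinuation or interruption at Day 5, or a Part 1 pause. Losing one active subject would not prevent escalation. The point is worth correcting because it concerns a binding threshold in a first-in-human study.

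**What to change.** In Section 5.2, item 19, change the limit from greater than 0.03 to greater than or equal to 0.03 mg/mg. In its second sentence, let the confirming measurement apply to a reading at or above the limit. Sections 4.6.1 and 5.4.3 stay as they are.

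The value on which a subject qualifies must then be below 0.03, while stopping remains at or above 0.03, so the two no longer overlap and 5.2 agrees with 4.6.1.

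The cost is two wording changes in one criterion. A few subjects at exactly 0.03 mg/mg would be screened out, and no procedure is added.
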